Primary Endpoint	
Acute Pain: Silverman Integrated Analgesic Assessment (SIA) score (a composite of pain and opioid usage) at 10 days post-surgery in participants who are genetically or pheno-converted CYP2D6 IM or PM
 
Chronic Pain: Pain control, defined as change in the composite pain intensity score from baseline to 3-months in participants who are genetically or pheno-converted CYP2D6 IM or PM
 
Depression: Depression symptom control, defined as change in PROMIS depression 8A scores from baseline to 3-months in genetically or pheno-converted CYP2D6 UM/PM or CYP2C19 UM/RM/PM

Secondary Endpoints	
Acute Pain:
 
 • Pain intensity at 10 days post-surgery • Opioid usage at 10 days post-surgery • Prescription pain medication misuse score 3 months post-surgery • Mobility score 1-month post-surgery • Opioid persistence 6 months post-surgery 
Chronic Pain:
 
 • Pain reduction magnitude at 3-month follow-up, relative to baseline • Achievement of clinically significant pain reduction (30%) by 3-month follow-up, relative to baseline • Prescription pain medication misuse score at 3-month follow-up 
Depression:
 
 • Change in PHQ-8 scores between baseline and 3 months • Achieve 50% reduction in PHQ-8 scores at 3 months, relative to baseline • Medication side effects severity burden at 3 months • Participant medication adherence at 3 months • Achieve remission at 6 months defined as PROMIS depression score ≤ 16 • Achieve remission at 6 months, defined as PHQ-8 score ≤ 4 
All Trials:
 
 • Overall well-being at 6 months in all randomized participants • Concordance between metabolizer phenotype and prescribed medication • Sub-domains of the PROMIS 43 survey: pain interference, physical function, sleep disturbance, social role and activities functioning, fatigue, anxiety, and depression at 6-month follow-up
Statistical Analyses	
Acute Pain:
 
 • The effect of genotype guided opioid therapy on pain control will be determined by comparing the 10-day post-surgery SIA scores of the Intervention arm participant with CYP2D6 IM or PM phenotypes to the 10-day post-surgery SIA scores of the Control arm participant with CYP2D6 IM or PM phenotypes using a two-sided t-test or a two-sided Mann Whitney

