3.2 Secondary Endpoints

Secondary endpoints include:

All Trials

1. Overall well-being at 6-month follow-up
2. Sub-domains of overall well-being: pain interference, physical function, sleep disturbance, social role and activities functioning, fatigue, anxiety, and depression at 6-month follow-up
3. Concordance between metabolizer phenotype and prescribed medication

Acute pain

1. Pain intensity at 10 days post-surgery
2. Opioid usage at 10 days post-surgery
3. Prescription pain medication misuse score at 3-months post-surgery
4. Mobility at 1-month post-surgery
5. Opioid persistence 6 months post-surgery

Chronic pain

1. Pain reduction magnitude at 3-month post return of genetic testing results to provider, relative to baseline
2. Proportion of participants achieving clinically significant pain reduction (30% reduction from baseline) at 3-months post return of genetic testing results to provider
3. Prescription pain medication misuse at 3-months post return of genetic testing results to provider

Depression

1. Change in PHQ-8 score between baseline and 3 months
2. Achieve 50% reduction in PHQ-8 scores at 3 months, relative to baseline
3. Medication side effects severity burden at 3 months
4. Participant medication adherence at 3 months
5. Achieve remission at 6 months, defined as PROMIS depression score ≤ 16
6. Achieve remission at 6 months, defined as PHQ-8 score ≤ 4

4. Study Arms & Design

This is a prospective, multicenter, subset analysis of 1:1 randomized Intervention (immediate PGx testing and genotype-guided opioid or SSRI therapy with clinical decision support) vs. Control (usual care with delayed PGx testing) pragmatic, open label clinical trial (Figure 1). The three trials are 1) genotype-guided opioid therapy among post-surgical acute pain participants (Acute Pain, Figure 1A), 2) genotype-guided opioid therapy among chronic pain participants (Chronic Pain, Figure 1B), and 3) genotype-guided SSRI therapy in participants with depression (Depression, Figure 1C). Trial-specific outcomes will be compared between participants in the intervention arm and control arms who have an actionable phenotype. Actionable phenotypes are defined as CYP2D6 IM and PMs (i.e. CYP2D6 activity score ≤ 0.75) for the acute pain and chronic pain trials and CYP2C19 UM, RM and PMs or CYP2D6 UM and PMs for the depression trial.

[figure not shown]

Figure 1. ADOPT PGx Trial Design

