PROMIS prescription pain medication mis-use scale - A participant completed survey of prescription medication misuse over the past 30 days. The survey is comprised of 7 questions on a 5-point ordinal scale of never/rarely/sometimes/frequently/almost always or not at all/a little bit/somewhat/quite a bit/very much[33]. This survey will be administered at baseline, 3 months, and 6 months post return of results.

PROMIS emotional distress depression 8b survey - A participant completed eight question survey assessing frequency of depression symptoms over the past 7 days[36]. This survey will be administered at baseline, 1 month, 3 months, and 6 months post return of results to the adult participants.

Opioid side effects – A participant completed survey of common opioid side effects experienced and the extent to which those side effects bothered the participant. This survey will be administered at baseline, 3 months, and 6 months post return of results to the adult participants.

Depression:

PROMIS emotional distress depression 8b survey - A participant completed eight question survey assessing frequency of depression symptoms over the past 7 days[36]. This survey will be administered at baseline, 1 month, 3 months, and 6 months post return of results to the adult participants.

PROMIS Pediatric Depressive Symptoms Short Form 8a- A pediatric (ages 8-17 years) participant completed eight question survey assessing frequency of depression symptoms over the past 7 days[37]. This survey will be administered at baseline, 3 months, and 6 months post return of results to the pediatric study participants .

Patient Health Questionnaire-8 – An 8 item survey completed by the participant assessing depression symptoms over the last two weeks. This survey will be administered at baseline, 3 months, and 6 months post return of results[38].

Antidepressant side effects – A participant completed survey of relevant antidepressant side effects. This survey will be administered at baseline, 1 month, 3 months, and 6 months post return of results.

Voils Medication Adherence - A participant completed three question survey, 5-point scale survey assessing participant medication adherence[39]. This survey will be administered to depression trial participants at baseline, 1 month, 3-months and 6 months post return of results.

All of the PROMIS® surveys can be found online[40].

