In prior studies of depression, the difference between study arms in PROMIS 8a T-scores was -6.7 with a SD of 10, for a standardized effect size of -.67. For the purposes of power analysis, a 4-point change is considered the minimally important difference representing a response to therapy that is congruent with the predicted CYP enzyme phenotype compared to the response to therapy which

conflicts with the phenotype.

Preliminary data from published studies indicate the proportion of participants with an actionable phenotype (CYP2C19 PM, RM, UM or CYP2D6 PM or UM, or pheno-converted CYP2D6 PM or UM) will be 40%. However, due to the distribution of study-related antidepressants in primary care and behavioral health settings, an estimated 67% of the participants with an actionable phenotype are anticipated to also have a study-related dosing or drug selection intervention. In other words, the analytic group of CYP2DC UM, PM, or CYP2C19 UM, RM, or PM phenotypes will represent a mixture of participants that may have a clinically meaningful change in depression due to being prescribed a study-relevant antidepressant and participants that may have changes in depression typical of the standard of care arm since they are not being prescribed a study-relevant antidepressant. In accounting for this population mixture, we incorporated a dilution factor of 67% into the clinically meaningful effect size projection and assume the effective difference of 0.28, representing a 2.8-point change to the T-score. We will need 542 modified intent to treat participants, 271 in each arm, to detect a standardized effect size of 0.28 with 90% power. After adjusting for the subset anticipated to have an actionable phenotype (i.e. 40%), 678 participants completing all assessments, per group, are required to achieve 90% power in the mITT analysis (1356 total). After accounting for 90% retention, 754 participants from the intervention arm and 754 participants from control arm (1508 total) are required to achieve 90% power for a two-sided two-sample t-test. Factoring in variability for the on the mITT proportion of the randomized population (40-60%), 1006-1508 randomized subjects would be needed to achieve 90% power in the mITT analysis.

Table 9. Sample size calculations

Sample size calculations for each trial, assuming an alpha of 0.049 to allow for one interim analysis

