The effect of genotype guided antidepressants therapy on the secondary endpoint depression remission and achieving 5% reduction in PHQ-8 scores will be assessed by comparing the Intervention group subset with CYP2D6 UM or PM or CYP2C19 UM, RM, or PM phenotypes the

Control group subset with CYP2D6 UM or PM or CYP2C19UM, RM, or PM phenotypes using a test of two-proportions with an alpha of 0.05. The effect of genotype guided antidepressants therapy on the secondary endpoints, medication adherence, PHQ-8 scores, and medication side effect severity burden, will be assessed by comparing the Intervention group subset with CYP2D6 UM or PM or CYP2C19 UM, RM, or PM phenotypes the Control group subset with CYP2D6 UM or PM or CYP2C19 UM, RM, or PM phenotypes using a two-sided Mann Whitney test with an alpha of 0.05. Participants that do not have metabolizer phenotypes will not be included in these analyses.

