11.2 Data Element Definitions

Clinically significant pain reduction: Whether or not the pain reduction score is ≤ 0.7 . If the pain reduction score is ≤ 0.7 , clinically significant pain reduction is achieved, if pain reduction scores is > 0.7 , clinically significant pain reduction is not achieved.

Depression symptom control: The change in the PROMIS Emotional Distress - Depression 8b or PROIMIS pediatric Depression 8a survey depression score from baseline to time t.

Depression remission: A. Whether or not the summed raw PROMIS emotional distress depression 8b survey responses are ≤ 16 , which is equivalent to the participant responding “rarely” or “never” to most or all of the PROMIS emotional distress - depression 8b survey questions. B. Whether or not the PHQ-8 scores are ≤ 4 , which is equivalent to depression severity being none-mild.

Depression (PHQ-8) score: The sum of the responses to the PHQ-8 survey, range from 0 to 24.

Depression (T) score: The T-score converted summed responses to the PROMIS emotional distress depression 8b survey. The T-score conversion is centered around 50 with standard deviation of 10.

Depression severity: The depression score converted to depression severity (none, mild, moderate, severe) based on the scoring guide for the PROMIS emotional distress depression 8b survey.

Medication adherence: The scored responses to the Voils Medication Adherence survey.

Medication concordance: Whether or not the medication the participant is prescribed after the intervention is concordant with the participants CYP2D6 and, for the depression trial, CYP2C19 phenotype.

Medication side effects severity burden: (Depression only) The sum of the scored severity (none = 0, mild = 1, moderate = 2, severe = 3) for common SSRI side effects.

Opioid misuse score: The T-score converted summed responses to the PROMIS prescription medication misuse 7a survey. The T-score conversion is centered around 50 with standard deviation of 10.

Opioid persistence: Defined as ≥ 1 opioid prescription refill between 90 days and 180 days after the surgical procedure.

Opioid usage: The average daily morphine equivalents in mg (MED) in past 7 days. MEDs will be calculated using data from the opioid usage survey.

Overall well-being: Defined as the T-score converted summed responses to the PROMIS 43/PROMIS 37 pediatrics survey. The T-score conversion is centered around 50 with standard deviation of 10.

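### Section 10.5 should name the PHQ-8 secondary endpoint as change from baseline to 3 months, as Section 3.2 does, and adjust it for baseline PHQ-8

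*Combined protocol and SAP*

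**What the plan says.** Section 3.2 lists the first depression secondary endpoint as "Change in PHQ-8 score between baseline and 3 months". The synopsis agrees: "Change in PHQ-8 scores between baseline and 3 months".

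The analysis text is in Section 10.5 (Depression). It says the effect "on the secondary endpoints, medication adherence, PHQ-8 scores, and medication side effect severity burden, will be assessed by comparing" the two actionable-phenotype subgroups, "using a two-sided Mann Whitney test with an alpha of 0.05". For PHQ-8 it mentions neither change, nor baseline, nor a visit.

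Section 11.2 gives this definition: "Depression (PHQ-8) score: The sum of the responses to the PHQ-8 survey, range from 0 to 24". It has no data element for PHQ-8 change, although it does define depression symptom control as a change for the PROMIS measure. Section 7.3 and Table 8 schedule PHQ-8 at baseline, 3 months and 6 months.

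**The concern.** Read together with Section 11.2, the label in Section 10.5 points to the raw item sum at an unstated visit, compared without adjustment. Section 3.2 points to a change score at 3 months. An analyst programming from Section 10.5 and one programming from Section 3.2 could produce different p-values for the same endpoint.

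Two features of the plan make this worth settling. Section 10.9 makes no multiplicity adjustment for secondary endpoints and relies partly on having prespecified the outcome variables, so the variable should be unambiguous where it is analysed. Section 10.6 (Depression) itself warns that baseline characteristics could differ between the intervention and control actionable subgroups. An unadjusted comparison of PHQ-8, on either scale, carries any baseline PHQ-8 difference into the result.

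**Working it through.** **The plan's own figure.** Section 10.1 states: "We will need 542 modified intent to treat participants, 271 in each arm, to detect a standardized effect size of 0.28 with 90% power". That calculation is for the PROMIS primary endpoint at two-sided alpha 0.049. The exact two-sample t calculation gives 270.4, hence 271 per arm and 542 in total, with power 0.901. The figure reproduces. No power or sample size is stated for PHQ-8.

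**How the two readings differ.** For each arm, mean change = mean 3-month score − mean baseline score. So the arm difference in raw 3-month score minus the arm difference in change is exactly the arm difference in baseline PHQ-8. With 271 per arm, the standard error of that baseline difference is √(2/271) = 0.086 baseline SD. A chance imbalance of that size separates the two estimates by 0.086 SD, about 31% of a 0.28 SD effect (0.086/0.28).

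**Inputs for the power illustration.**
- 271 per arm (Section 10.1) and two-sided alpha 0.05 (Section 10.5).
- Effect of 0.28 SD of the 3-month score. This is borrowed from the PROMIS primary; the documents give no PHQ-8 effect.
- Equal SDs at both visits, normal data, and r = 0.3 to 0.7. These are assumptions; the documents give no PHQ-8 SD or correlation.

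**Formulas.** Relative to the variance of the raw 3-month score:
- unadjusted change: 2(1 − r)
- 3-month score adjusted for baseline: 1 − r²

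The effective standardized difference is 0.28/√(relative variance). Power is from the noncentral t distribution.

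| r | Variance, change | Variance, adjusted | Effect, change | Effect, adjusted | Power, raw | Power, change | Power, adjusted |
|---|---|---|---|---|---|---|---|
| 0.3 | 1.40 | 0.91 | 0.237 | 0.294 | 90.2% | 78.5% | 92.7% |
| 0.5 | 1.00 | 0.75 | 0.280 | 0.323 | 90.2% | 90.2% | 96.4% |
| 0.7 | 0.60 | 0.51 | 0.361 | 0.392 | 90.2% | 98.7% | 99.5% |

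For the planned Mann-Whitney test under normality (n multiplied by 3/π), power is 89% for the raw score and 77%, 89% and 98% for change at the same three correlations. The pattern is the same.

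**Equal power is not equal results.** In two runs of 4,000 simulated trials per correlation (same n and effect, Mann-Whitney on each version), the raw-score and change tests fell on opposite sides of 0.05 in about 20–22%, 14–15% and 11–13% of trials at r = 0.3, 0.5 and 0.7.

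**Why adjustment does not change the endpoint.** If the 3-month score is modelled as a + b × baseline + t × arm, subtracting baseline from both sides gives change = a + (b − 1) × baseline + t × arm. The arm coefficient t is the same, so the adjusted model estimates the difference in change that Section 3.2 asks for. Its variance is never larger than either alternative under the stated assumptions: 1 − r² ≤ 1, and 1 − r² = (1 − r)(1 + r) ≤ 2(1 − r).

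**The case against.** A reader might infer that the plan prespecifies two versions of this endpoint, or that Section 10.5 never analyses the one in Section 3.2. The documents do not support that. Section 10.5 presents its list as the secondary endpoints, meaning those already defined, and the synopsis and Section 3.2 define only one continuous PHQ-8 endpoint. The synopsis also says that all depression secondary endpoints will be compared between these subgroups. Short labels without time points are usual in Section 10.5: adherence, side-effect burden, remission and most of the acute pain endpoints appear that way. The entry in Section 11.2 says how the instrument is scored; it does not create an endpoint. Section 10.2 also places the detailed plan for each trial in a separate document, which may settle the matter.

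Most of this stands, and it reduces the point to a request for explicit wording. What it does not remove is that PHQ-8 is the one item in its list where the short form drops more than the visit. Adherence and side-effect burden are levels in Section 3.2, whereas PHQ-8 is a change, and its short form has its own definition as a raw sum. Section 10.4 writes out change in full for the primary endpoint, and Section 10.5 does analyse raw 6-month T-scores for well-being, so the raw reading is not far-fetched.

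It can also be objected that baseline adjustment is a change of method which the wording mismatch does not require, and that its efficiency is shown here only under normality, not against a rank test on a sum bounded at 0 and 24. Both points are fair. The adjustment is recommended on its own merits, and a rank analysis should be kept alongside it.

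**Conclusion.** The endpoint itself is defined consistently in the synopsis and Section 3.2. The defect is that Section 10.5 labels it in a way that, with Section 11.2, also fits an unadjusted raw-score comparison. That should be made explicit, because the two analyses can give different answers on the same data.

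It would be tempting to conclude that one reading is less powerful. The documents do not support this: below r = 0.5 change has less power than the raw score, above it more, and r is not given. What does hold across the assumed range is that the baseline-adjusted analysis does at least as well as either: 93% to 99.5%, against 90% for the raw score and 78% to 99% for unadjusted change. These figures rest on normality, equal SDs, an effect size borrowed from the PROMIS primary and an assumed r of 0.3 to 0.7. They illustrate the comparison and do not predict the power of this endpoint.

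The point concerns one secondary endpoint. The primary analysis and the 542-participant calculation are untouched.

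**What to change.** 1. In Section 10.5 (Depression), replace the PHQ-8 label with *change in PHQ-8 score from baseline to 3 months*, and add a matching data element to Section 11.2.
2. Estimate the arm difference, with its confidence interval, from a linear model of the 3-month PHQ-8 score with arm and baseline PHQ-8 as terms.
3. Because the score is bounded at 0 to 24, keep the planned Mann-Whitney test, applied to change, or a rank-based baseline-adjusted version, as a sensitivity analysis.
4. Carry the same wording into the depression trial's separate SAP.

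Cost: item 1 is wording only. Items 2 and 3 change the main test for one secondary endpoint, so they should be recorded as such and settled before PHQ-8 is compared by arm. No new data are needed, since baseline PHQ-8 is already scheduled, and the sample size does not change.

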10.6 Other Planned Analyses

Exploratory endpoints or comparisons of endpoints that will be considered:

- Medication side effects
- Comparisons of measures of depression and/or pain
- Provider actions taken after CDS alerts

Sub-groups that will be considered:

- All randomized participants
- Metabolizer phenotypes: UMs, RMs, NMs, IMs, and PMs.
- CYP2D6 or CYP2C19 activity scores
- Pediatric participants
- Adult participants
- “Per-protocol” - participants with both an actionable phenotype and concordance between the recommended medication/dosage and the prescribed medication and/or dosage
- Participants with an actionable phenotype, a discordant medication at baseline, and a concordant medication at the end of the study
- Stratified by medication, medication class and/or medications combinations
- Stratified by demographic characteristics (e.g. age, sex, gender and/or race)
- Stratified by type and/or design of CDS implemented
- Stratified by institution, enrolling site, and/or practice setting specialty (e.g. psychiatry, primary care, etc.)
- And other relative combinations of the above sub-groups

In addition to the primary research exploratory analyses, we will also analyze the uptake and utilization of the clinical decision support (CDS) tools that were created and its role in any medication changes made by providers. We will examine the impact of the CDS tools on various primary and secondary outcomes. We may also describe the development of the CDS tools, with a specific focus on the automated phenoconversion calculations implemented by some sites. As part of these analyses, we may collect and/or include the following data points: socio-demographics, health care characteristics (i.e. comorbidities), site ID, clinical group ID, CDS related data points (i.e. alert ID, CDS name, CDS alert type, date triggered, provider action), prescriber specialty, medication details (i.e. triggering medications, medication or dose changes, medication concordance/discordance), genotype and phenoconversion results.

We will also analyze reach, adoption, and implementation of the trial and PGx testing. We will examine enrollment and screening information, missing data rates, visit completion information. We will also analyze patient preferences for contact and survey administration, in addition to survey completion information

Specified analyses:

All Trials

Medication side effects. The frequency and severity of medication side effects within each trial and trial arm will be summarized using standard descriptive statistics for discrete data (counts and percentages).

Acute Pain

Trends in endpoints. In addition to the primary and secondary endpoints described above, we will compare the time trends in the endpoints: pain scores, opioid usage, opioid misuse score, and mobility score at baseline, 1, 3, and 6 months among the CYP2D6 IM or PM subgroup, using a repeated-measures mixed effect model or generalized repeated-measures mixed effect model, as appropriate. Since participants are randomized to Intervention and Control groups and not to the CYP2D6 IM or PM subgroup within Intervention and Control groups, there could be important differences in baseline characteristics between the two groups. For these reasons, we will conduct covariate-adjusted repeated measures mixed models that will account for differences in baseline characteristics that differ between the Intervention – CYP2D6 IM or PM subgroup and the Control – CYP2D6 IM or PM subgroup. Potential baseline characteristics may include age, sex, income, education, insurance, surgical procedure type. We will select the appropriate covariance matrix (e.g. compound symmetry, autoregressive, unstructured, or other covariance structure) based on the data.

Difference within the NM group. In the control arm participants, we will compare pain scores in participants with a CYP2D6 activity score $>0.75 - 1$ to participants with an activity scores $>1-2$ using a two-sided two-sample t-test or Mann Whitney test, as appropriate, with a type 1 error of 0.05. Additionally, we will use linear regression to adjust for differences in baseline characteristics.

Chronic Pain

Trends in endpoints. In addition to the primary and secondary endpoints described above, we will compare the time trends in the endpoints: pain control, pain reduction, clinically significant pain reduction, and opioid misuse score at baseline, 1, 3, and 6 months among the CYP2D6 IM or PM subgroup, using a repeated-measures mixed effect model or generalized repeated-measures mixed effect model, as appropriate. Since participants are randomized to Intervention and Control groups and not to the CYP2D6 IM or PM subgroup within Intervention and Control groups, there could be important differences in baseline characteristics between the two groups. For these reasons, we will conduct covariate-adjusted repeated measures mixed models that will account for differences in baseline characteristics that differ between the Intervention – CYP2D6 IM or PM subgroup and the Control – CYP2D6 IM or PM subgroup. Potential baseline characteristics may include age, sex, income, education, insurance, and medical conditions. We will select the appropriate covariance matrix (e.g. compound symmetry, autoregressive, unstructured, or other covariance structure) based on the data.

Difference within the NM group. In the control arm participants, we will compare pain scores and pain control in participants with a CYP2D6 activity score $>0.75 - 1$ to participants with an activity scores $>1-2$ using a two-sided two-sample t-test or Mann Whitney test, as appropriate, with a type 1 error of 0.05. Additionally, we will use linear regression to adjust for differences in baseline characteristics.

Depression

Trends in endpoints. In addition to the primary and secondary endpoints described above, we will compare the time trends in the endpoint depression symptom scores at baseline, 1, 3, and 6 months among the CYP2D6 PM or UM or CYP2C19 UM, RM or PM subgroup, using a repeated-measures mixed effect model. Since participants are randomized to Intervention and Control groups and not to the CYP2D6 PM or UM or CYP2C19 UM, RM or PM subgroup within Intervention and Control groups, there could be important differences in baseline characteristics between the two groups. For these

reasons, we will conduct covariate-adjusted repeated measures mixed models that will account for differences in baseline characteristics that differ between the Intervention – CYP2D6 PM or UM or CYP2C19 UM, RM or PM subgroup and the Control – CYP2D6 PM or UM or CYP2C19 UM, RM or PM subgroup. Potential baseline characteristics may include age, sex, income, education, insurance, medical conditions. We will select the appropriate covariance matrix (e.g. compound symmetry, autoregressive, unstructured, or other covariance structure) based on the data.

Difference within the NM group. In the control arm participants, we will compare depression scores and depression control in participants with a CYP2D6 activity score $>0.75 - 1$ to participants with an activity scores $>1-2$ using a two-sided two-sample t-test or Mann Whitney test, as appropriate, with a type 1 error of 0.05. Additionally, we will use linear regression to adjust for differences in baseline characteristics

Cost Effectiveness

Healthcare costs: In the Medicare fee-for-service or Medicaid enrollees, log-transformed overall expenditures (between index visit and 6 months follow-up) will be compared using a 2-sample t-test between the study arms (after ensuring that the variances in the log-scale are equal). Alternatively, cost comparisons will be made using appropriate regression models such as generalized linear models. For all participants, regardless of insurance type, we will estimate and aggregate participant-reported healthcare utilization during follow-up and assign cost for each item based on unit weighted mean cost estimates from the Medicare/ Medicaid data.

Within the Medicare/Medicaid population, we will compare estimated cost differences between genotype-guided and usual care based on billing records versus participant report to further validate the cost comparisons for the entire population. Cost for the index hospitalization for surgery participants will not be included in the cost estimate, but we will compare length of stay between groups as reference for hospitals regarding potential cost savings in capitation-based reimbursement schemes. All costs will be converted to 2021 \$US using the chain-weighted Consumer Price Index (CPI).

Finally, we will compare the Medicare/Medicaid beneficiaries among our trial enrollees to a larger random sample of beneficiaries in the participating states and compare demographic and key clinical characteristics to explore representativeness of our study sample, evaluate the impact of attrition and loss to follow-up and make inferences about the generalizability of our results.

Cost utility: For the cost-utility analysis, the PROMIS-43 responses will be converted into utilities using previously validated crosswalks.[41] Cost and quality adjusted life year (QALY) estimates, adjusted for clustering within site and baseline utility for QALYs, will be obtained using appropriate regression models such as generalized linear models. The analysis of maximum likelihood parameter estimates will allow us to capture differences in cost and QALYs between the intervention arm and control arm of the trial. The Incremental cost-effectiveness ratio (ICER) will be calculated from costs and QALY. A bootstrapping approach will be used to characterize sampling uncertainty and calculate confidence intervals (CI) around the ICER estimate (2.5th and 97.5th percentiles corresponding to the lower and upper bounds of the CI, respectively). This sampling uncertainty will be summarized using cost-effectiveness acceptability curves.

Details of these statistical analyses, along with other exploratory analyses will be described in the study SAP.

